5.4.1 Data Collection and Follow-up for Withdrawn Subjects

Table 1. Interim pilot results		
Question	Prevalence	Sensitivity
Fever	0.021	1.00 (0.03-1.00)
Fatigue	0.426	1.00 (0.83-1.00)
Pain	0.163	0.43 (0.10-0.82)
Rash	0.071	0.33 (0.01-0.91)
Itching	0.071	1.00 (0.30-1.00)
Dizziness	0.024	1.00 (0.03-1.00)
Neuropathy	0.00	
Weakness	0.024	1.00 (0.03-1.00)
Vision change	0.049	1.00 (1.16-1.00)
Headache	0.024	1.00 (0.03-1.00)
Shortness of breath	0.024	1.00 (0.03-1.00)
Cough	0.049	0.50 (0.01-0.99)
Nausea	0.125	1.00 (0.48-1.00)
Vomiting	0	
Diarrhea	0.125	1.00 (0.48-1.00)
Constipation	0.025	1.00 (0.30-1.00)
Loss of appetite	0.075	1.00 (0.30-1.00)
Summary	0.532	1.00 (0.863-)

CONFIDENTIAL

This material is the property of the University of Pennsylvania.

Even though subjects may be withdrawn prematurely from the study, it is critical that we understand potential reasons for subject withdrawal which could indicate issues regarding the intervention's feasibility or acceptability for future work. Therefore, participants who have withdrawn consent will be seen for one final study visit during which time they will be asked to complete final study questionnaires as well as an open-ended question regarding reasons for study discontinuation.

score		1.00)
-------	--	-------

6 Statistical Plan

6.1 Sample Size and Power Determination

AIM 1 Pilot study: This protocol describes a cross-sectional study designed to investigate the operating characteristics of a text-based e-triage to capture patients experiencing immune-related adverse events against the gold standard of documented toxicity assessments in the EMR. Due to the granular nature of our e-triage questionnaire we believe a sensitivity of 95-100% is very reasonable to anticipate.

Results from the interim analysis including 48 patients are shown in Table 1. Median age was 68.5 (IQR 58-72), 58% were female, 88% white, and most patients either had thoracic (25%), genitourinary (27%), head/neck (15%), or skin (15%) cancers. 53.2% of patients had at least 1 toxicity related adverse event documented in the EMR. Sensitivity to identify at least one toxicity related adverse event was 100% (95% CI 0.863-1.00) aligning with our primary endpoint. Despite being at our target sensitivity we identified two underperforming questions (pain and rash) and therefore optimized the instrument creating a version 2 (see appendix). Assuming the sensitivity and prevalence are same as those in the preliminary data, a sample of 47 patients will produce adequate precision for the estimate for sensitivity, with the half width of the 95% confidence interval no larger than 7%.

AIM 2 Randomized control trial: We plan to enroll 176 patients and expect to have 160 patients left assuming a 10% drop out rate (e.g., due to disease progression and need to change therapy). Based on the preliminary data recently published by this group measuring total care time of patients treated at the Penn Abramson Cancer Center⁸, we expect the total care time in the control group to have a mean of 130 hours with a SD of 118. A sample size of 80 per group will provide 79% power to detect a 40% reduction in the total care time (130 vs. 78) assuming a type I error rate of 0.05.

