6.2 Statistical Methods

Aim 1 Pilot study: Sensitivity and specificity will be calculated along with exact 95% confidence intervals (CIs). Sensitivity will be calculated as the proportion of patients with toxicity captured by the text-based e-triage among patients with toxicity as documented by the provider in the EMR. Specificity will be calculated as the proportion of negative e-triage screens among patients without symptoms as documented by the provider in the EMR. We will additionally be performing a series of psychometric analyses including response distribution to assure responses are not skewed, item-scale correlation, internal consistency, floor and ceiling effects and item reduction as well as response rates.

Table 2. Power to detect reduction in total care time (N=160)	
Reduction in care time	Power
35%	68%
40%	79%
45%	88%
50%	93%

AIM 2 Randomized control study: Standard descriptive statistics will be calculated to compare patient characteristics for the intervention arm versus the control arm, such as medians and interquartile ranges for continuous variables and frequencies and proportions for categorical variables. These characteristics will be compared between the two groups using the Wilcoxon rank sum test for continuous variables and the chi squared or Fisher's exact test for categorical variables. We expect these characteristics will be similarly distributed between the intervention groups due to randomization, but in the case of imbalance, they may be adjusted in the multivariable model of the outcome.

The primary analyses will be Intent-to-Treat, with the primary outcome (total care time) compared using a

CONFIDENTIAL

two-sample t test, or Wilcoxon test if normal distribution assumption is violated. A multivariate linear regression will be used to adjust potential confounders including demographics (age, gender, race, SES), comorbidities (Elixhauser comorbidity index), treatment intent (curative versus palliative), and performance status. The final model will be established using stepwise forward regression based on 10% change in effect estimate for intervention. As a secondary analysis, “as treated” analyses will be performed to account for permissive non-adherence to the triage assignment. Standard descriptive statistics will be used to describe patient factors associated with more frequent triage non-adherence.

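### Is the Aim 1 precision claim, a half-width of at most 7% for sensitivity with 47 patients, too favourable?

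*Protocol*

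**What the plan says.** Protocol 6.1 (Aim 1), repeated word for word in SAP 1.1, reports the interim pilot data and then gives the planned precision.

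- **Interim prevalence:** "53.2% of patients had at least 1 toxicity related adverse event documented in the EMR".
- **Interim sensitivity:** "Sensitivity to identify at least one toxicity related adverse event was 100% (95% CI 0.863-1.00", with the interval closing at 1.00.
- **Condition on the precision statement:** "Assuming the sensitivity and prevalence are same as those in the preliminary data".
- **Sample:** "a sample of 47 patients will produce adequate precision for the estimate for sensitivity".
- **Precision:** "with the half width of the 95% confidence interval no larger than 7" percent.

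Earlier in the same section, in a separate sentence, the plan says "we believe a sensitivity of 95-100% is very reasonable to anticipate". Protocol 6.2 and SAP 1.2 specify exact 95% intervals and define the denominator of sensitivity as those "among patients with toxicity as documented by the provider in the EMR".

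**The concern.** An upper limit on the half-width reads like a guarantee, and two things could break it. First, 47 is the number of all pilot patients, while sensitivity uses only those with documented toxicity. That number is not fixed in advance, and with 24 instead of 25 the half-width already passes 7%. Second, the figure is worked out at 100% sensitivity, where the exact interval is narrowest. The section itself regards 95% as plausible, and a single miss among 25 takes the half-width to about 10%.

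A half-width also describes a one-sided situation poorly. When the estimate is 100%, the whole width lies below it, so a quick reader might take 7% to mean a lower limit near 93% when it is 86%.

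This would matter because the sentence is the only justification given for 47 patients on the Aim 1 endpoint. In the randomized trial the instrument decides who goes to infusion without an office visit (Protocol 5.2.2). A false precision claim here would overstate what the pilot can show about missed toxicity.

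**Working it through.** **Inputs.** Sample of 47, prevalence 0.532 and sensitivity 1.00 (Protocol 6.1, SAP 1.1); exact two-sided 95% interval, with patients who have toxicity as denominator (Protocol 6.2, SAP 1.2).

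**1. The plan's own figure.**

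- Expected number with toxicity: 47 × 0.532 = 25.0.
- All n detected: the exact lower limit is 0.025^(1/n) and the upper limit is 1.
- n = 25: 0.025^(1/25) = 0.8628.
- Half-width: (1 − 0.8628)/2 = 0.0686, or 6.86%.

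This reproduces both the printed limit of 0.863 and the 7%.

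The text gives 48 interim patients, whereas 53.2% is 25/47 (25/48 would be 52.1% and 26/48 would be 54.2%). The result is unaffected.

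**2. Number with toxicity allowed to vary, sensitivity kept at 100%.** Let K be binomial (47, 0.532). Its 10th, 50th and 90th percentiles are 21, 25 and 29.

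| Detected / with toxicity | Exact 95% CI | Half-width |
|---|---|---|
| 26/26 | 0.868–1.000 | 6.6% |
| 25/25 | 0.863–1.000 | 6.9% |
| 24/24 | 0.858–1.000 | 7.1% |
| 23/23 | 0.852–1.000 | 7.4% |
| 21/21 | 0.839–1.000 | 8.1% |

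The chance that K is 24 or fewer is 0.44, so the half-width is 7% or less with probability 0.56. Averaged over K, it is 6.97%. The shortfall at the 10th percentile is 8.1 − 7.0 = 1.1 percentage points.

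**3. Sensitivity below 100%, outside the stated condition.** With 25 patients who have toxicity:

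- one miss (24/25): 0.796–0.999, half-width 10.1%;
- two misses (23/25): 0.740–0.990, half-width 12.5%;
- chance of at least one miss: 1 − 0.98^25 = 0.40 at 98% sensitivity, and 1 − 0.95^25 = 0.72 at 95%.

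With K also varying, the results are:

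| True sensitivity | Chance of half-width ≤ 7% | Expected half-width |
|---|---|---|
| 100% | 0.56 | 7.0% |
| 98% | 0.32 | 8.5% |
| 95% | 0.14 | 10.5% |

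One miss stays within 7% only from 38 patients with toxicity (37/38: half-width 6.87%), which has a probability of about 0.00008 among 47.

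**4. What the sentence claims.** It fixes sensitivity and prevalence at the interim values, which is step 1, and the figure is right there. Step 2 adds sampling variation in K, which the sentence does not model, and the average still comes within 7%. Step 3 changes the sensitivity that the sentence holds fixed.

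**The case for a change.** The strongest contrary argument is that a population prevalence of 53.2% does not give exactly 25 patients with toxicity. Even with both assumptions granted, the limit is exceeded 44% of the time. The plan also changed the questionnaire to a second version after the interim look, so an unchanged sensitivity of 100% is itself an assumption, and no other scenario is shown. The quantity that matters for safety is the lower confidence limit, which a half-width hides.

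The arithmetic in this argument is correct, but it does not show the sentence to be false. Putting the expected count into a precision calculation is ordinary planning practice. The 44% counts results such as 7.1% and 7.4% as failures, so it makes a small excess look like a coin toss. Planning at 100% is not arbitrary: it is the hypothesis in Protocol 2.1 (H1), the stated target and the interim result. The 95–100% expectation is a different sentence, and no precision is attached to it.

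The change of version does make the 100% an assumption, but the plan declares it as one. The lower limit is not hidden either, since 0.863 appears in the same paragraph and in Table 1.

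What stands is that the plan shows no precision for any sensitivity below 100%, where it is clearly worse. Limits of about 80% with one miss and 74% with two would be useful to a reader. That is an optional addition.

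**Conclusion.** The concern does not hold. The 7% is a correctly calculated figure under a condition stated in the same sentence: 25 of 25 detected, half-width 6.86%. If the number with toxicity varies at 100% sensitivity, the half-width averages 6.97% and is 8.1% at the 10th percentile.

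The larger departures (10.1% with one miss and 12.5% with two, among 25) arise only when the sensitivity condition is dropped, and the plan makes no claim there. Nothing depends on the 7%: "Sensitivity and specificity will be calculated along with exact 95% confidence intervals (CIs") is already the planned analysis, so the precision actually achieved will be reported for whatever counts occur, and no decision rule in the documents refers to the figure. Rewording it would change no patient number, analysis or conclusion.

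This rests on reading the sentence together with its opening condition, on exact (Clopper-Pearson) intervals as specified, and on a binomial count of patients with toxicity for the variability check.

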6.2 Statistical Methods

Aim 1 Pilot study: Sensitivity and specificity will be calculated along with exact 95% confidence intervals (CIs). Sensitivity will be calculated as the proportion of patients with toxicity captured by the text-based e-triage among patients with toxicity as documented by the provider in the EMR. Specificity will be calculated as the proportion of negative e-triage screens among patients without symptoms as documented by the provider in the EMR. We will additionally be performing a series of psychometric analyses including response distribution to assure responses are not skewed, item-scale correlation, internal consistency, floor and ceiling effects and item reduction as well as response rates.

Table 2. Power to detect reduction in total care time (N=160)	
Reduction in care time	Power
35%	68%
40%	79%
45%	88%
50%	93%

AIM 2 Randomized control study: Standard descriptive statistics will be calculated to compare patient characteristics for the intervention arm versus the control arm, such as medians and interquartile ranges for continuous variables and frequencies and proportions for categorical variables. These characteristics will be compared between the two groups using the Wilcoxon rank sum test for continuous variables and the chi squared or Fisher's exact test for categorical variables. We expect these characteristics will be similarly distributed between the intervention groups due to randomization, but in the case of imbalance, they may be adjusted in the multivariable model of the outcome.

The primary analyses will be Intent-to-Treat, with the primary outcome (total care time) compared using a

CONFIDENTIAL

two-sample t test, or Wilcoxon test if normal distribution assumption is violated. A multivariate linear regression will be used to adjust potential confounders including demographics (age, gender, race, SES), comorbidities (Elixhauser comorbidity index), treatment intent (curative versus palliative), and performance status. The final model will be established using stepwise forward regression based on 10% change in effect estimate for intervention. As a secondary analysis, “as treated” analyses will be performed to account for permissive non-adherence to the triage assignment. Standard descriptive statistics will be used to describe patient factors associated with more frequent triage non-adherence.

Secondary endpoints include: total wait time measured, total number of hospitalization/emergency department encounters, patient satisfaction [The Patient Satisfaction Questionnaire Short Form (PSQ-18)]¹, provider satisfaction (Net-Promoter Score)^{2,3}, and health related quality of life [Functional Assessment of Cancer Therapy-General (FACT-G)⁴]. Total wait time and number of hospitalizations will be compared between groups using Wilcoxon rank sum test. The rest of the secondary endpoints will be measured at multiple time points and longitudinal linear mixed-effects model will be used to compare the group difference over time. Additional secondary analyses exploring changes in visit time across the duration of follow-up will also be performed.

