3.3 Study Measures

AIM 1 Pilot study:

- **E-triage:** The e-triage will consist of 16 questions, modified from the validated NCI Pro-CTCAE™, which will be sent to patients via WaytoHealth®'s two-way texting system 96 hours prior to their scheduled immunotherapy infusion (see appendix B). Questions will pertain to common or emergent immune related adverse events as defined by the NCCN guidelines and two senior disease experts⁴²⁻⁴⁴. Patients will be prompted via text to measure the presence and severity of symptoms over the week prior. A final question will be included to capture any additional symptoms patients wish to disclose.
- **NCI Pro-CTCAE™:** A subset of patients may be asked to fill out a subset of the NCI PRO-CTCAE™, a set of validated questions for the collection of patient-reported outcomes to capture symptomatic adverse events in patients on cancer clinical trials, in order assess construct validity.
- **Definition of gold standard:** Patient reported toxicity captured by the text-based instrument will be compared to provider reported toxicity as documented in the EMR as the gold standard. To assess provider reported toxicity, standardized abstraction protocols will be developed by the PI and implemented by trained research staff.

AIM 2 Randomized control study:

- **Care time:** Care time will be defined as total time spent commuting to and receiving cancer care (including time spent obtaining labs). This will be captured using a combination of time-stamp information abstracted from AirFinder®, a real time patient located system deployed in the Perelman Cancer Clinics, and self-reported time for commuting and time spent obtaining local labs. Commute times will also be estimated using the patient's home address geocoded using ArcGIS software.
- **Emergency department and hospitalization rates:** Total number of emergency department visits and hospitalizations will be collected using data abstracted from the Penn electronic medical record during a 3 month follow-up window as well as through patient check-ins with study staff during routine infusion visits to account for care received outside the Penn system.

CONFIDENTIAL

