3.4.1 Primary Study Endpoint

AIM 1 Pilot: To assess the performance of the text-based e-triage system sensitivity and specificity with a gold standard will be determined.

AIM 2 Randomized control trial: The primary endpoint will be cumulative care time associated with cancer treatment, measured over a over three months or at least 3 infusion visits. We will define care time as total time spent commuting to and receiving care (including time spent obtaining labs).

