7.1 Definitions

7.1.1 Adverse Event

An adverse event (AE) is any symptom, sign, illness or experience that develops or worsens in severity during the course of the study. Intercurrent illnesses or injuries should be regarded as adverse events. Abnormal results of diagnostic procedures are considered to be adverse events if the abnormality:

- results in study withdrawal
- is associated with a serious adverse event
- is associated with identification clinical signs or symptoms
 - This will be defined as immune related adverse events, per the NCCN guidelines regarding management of immune related adverse events⁴⁴, that result in treatment holds or steroid initiation.
 - Delayed identification of immune related adverse events, defined by symptoms or lab abnormalities that preceded a treatment infusion that was missed by e-triage or an office visit, will be documented separately.

CONFIDENTIAL

- leads to additional treatment or to further diagnostic tests
- is considered by the investigator to be of clinical significance

The objective of the pilot study is to optimize the questionnaire to quickly identify cancer related symptoms and immune related adverse events.

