7.4.2 Data and Safety Monitoring Plan

Overall data and safety will be monitored on an ongoing basis by the PIs and the study team. As needed, the investigators may decide to appoint an independent medical monitor to evaluate adverse events and make recommendations for continuing or stopping a trial. No interim analysis will be conducted.

Monitoring e-triage: All Waytohealth© interactions will be input into a flowsheet embedded into the patient's EMR and available to all study and clinical staff. All relevant persons will be notified via an EMR alert when any new information is entered. Dedicated research staff will be monitoring for inputs daily and will interphase with the research PI as well as clinical team as needed for unanticipated responses or symptoms. Any identified symptom will require the patient to have an in-person assessment with their routine clinical team. Clinical staff will be notified of the patient's triage status and offered the opportunity to mandate an in-person assessment regardless of the patient's triage status. A patient's enrollment in the study will be terminated if they experience an emergency medical situation requiring intervention or violate study protocol.

Monitoring clinical events: Research staff will see patients at each of their infusion visits. During this time, they will assess for any unidentified immunotherapy adverse events as well as screen for any emergency department visits or hospitalizations which occurred outside the Penn system. Additionally, research staff will receive EPIC alerts corresponding to any emergency department visits or hospitalizations.

8 Study Administration, Data Handling and Record Keeping

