10.1 Risks

AIM 1 Pilot study: Potential study risks are expected to be minimal. There is a minor risk of loss of confidentiality and privacy. The research team will take the necessary precautions to ensure that confidentiality and privacy are maintained. We will use commercial-grade encryption to protect participating information similar to that which is used to protect electronic medical records. Personal information will be used only by study team members who have been trained to use secure protocols to maintain the privacy of your data. Whenever possible, data will be de-identified to protect privacy. We will link individual identifying information with participant ID numbers in one secure file that will only be accessed by the study team in the case of an adverse medical event, participant dropout, or if otherwise deemed necessary by the Principal Investigator. All other identifying information will be discarded after initial contact with the research coordinator. Due to the fact, all patients will be seeing their provider with standard laboratory testing within 4 days of the questionnaire we feel that there is minimal physical risk to patients.

AIM 2 Randomized control trial: As above, there is a minimal risk of loss of confidentiality and privacy. The second potential risk is that participants misinterpret the e-triage as a means of quick communication with their care team. We will take great care to emphasize that the e-triage system is investigational, and not a replacement for usual means of communication with one's care team. Participants will be reminded repeatedly both verbally and via text after each questionnaire that they should contact their care team directly if they are having any symptoms for which they think urgent medical attention is warranted. There is also a risk of participants inappropriately, or incompletely, filing out the e-triage questionnaire. We hope to minimize this risk via the execution of the pilot study. Patients who do not fill out the questionnaire completely will therefore not be eligible to be fast-tracked to avoid an incomplete symptom assessment. Patients will be screened, per routine standard of care, by laboratory tests and vital sign assessments. Research staff will see patients at each infusion as well for toxicity assessments. Finally, patients or providers will be offered the opportunity to override the system and request in-person assessment.

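### Aim 1 specificity is taken among patients without documented symptoms, while sensitivity is taken among patients with documented toxicity, so the two groups need not be complements

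*Protocol*

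**What the plan says.** The Aim 1 endpoint in protocol 3.4.1 covers both measures: "To assess the performance of the text-based e-triage system sensitivity and specificity with a gold standard will be determined". Protocol 3.3 names the reference: "Patient reported toxicity captured by the text-based instrument will be compared to provider reported toxicity as documented in the EMR as the gold standard".

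Protocol 6.2 then defines the two estimates in consecutive sentences:

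- Sensitivity: "Sensitivity will be calculated as the proportion of patients with toxicity captured by the text-based e-triage among patients with toxicity", with toxicity as documented by the provider in the EMR.
- Specificity: "Specificity will be calculated as the proportion of negative e-triage screens among patients without symptoms as documented by the provider in the EMR".

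The Study Summary and SAP 1.2 repeat both definitions. No section says that *symptoms* and *toxicity* mean the same thing. The abstraction rules that might settle it are, according to protocol 3.3, still to be developed.

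Two further statements bear on who screens positive. Under protocol 3.3 the text prompts ask patients to "measure the presence and severity of symptoms over the week prior". For the trial, protocol 7.4.2 says: "Any identified symptom will require the patient to have an in-person assessment with their routine clinical team".

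**The concern.** Sensitivity and specificity against one reference standard should divide the evaluable patients into two groups, reference-positive and reference-negative. Here the positive group is defined by toxicity and the negative group by absence of symptoms. If the terms differ, a third group is left over: patients with a documented symptom, for example from the cancer itself, that the provider does not record as toxicity.

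That group matters because the instrument asks about symptoms. Its members are the toxicity-free patients most likely to be flagged, that is, the likeliest false positives. Leaving them out of the denominator would remove false positives from a component of the Aim 1 primary endpoint, and an abstractor who follows the text literally would do so.

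**Working it through.** **1. The plan's own figures.** Protocol 6.1 gives 53.2% of patients with documented toxicity and a sensitivity of 100% (exact 95% CI 0.863-1.00).

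- 25/47 = 0.532. With a denominator of 48, the nearest values are 25/48 = 0.521 and 26/48 = 0.542, so the figure fits 47 evaluable patients.
- For 25/25 the exact lower limit is 0.025^(1/25) = 0.863, and the half-width is (1 - 0.8628)/2 = 0.069. Both the printed interval and the planned half-width of at most 7% reproduce.

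Sensitivity is therefore sound as written, and nothing below changes it.

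**2. The group without toxicity.** 47 - 25 = 22 patients. The documents give no specificity, no count of negative screens, and no count of patients with symptoms but no toxicity. What follows is therefore conditional.

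**3. Formula.** Of the 22, let *s* have a documented symptom not recorded as toxicity. Let *p* be the proportion screening negative among the other 22 - *s*, and *f* the proportion among the *s*.

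- As written: specificity = *p*.
- Among all toxicity-free patients: specificity = [(22 - *s*)*p* + *s f*]/22.
- Difference: *s*(*p* - *f*)/22.

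The difference is zero if *s* = 0 or *f* = *p*, and positive (specificity as written too high) if symptomatic patients screen negative less often than the rest.

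**4. Illustration.** Assume that all *s* are flagged (*f* = 0) and that 2 of the other patients are flagged. Intervals are exact 95% limits.

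| *s* | As written | Among all 22 without toxicity |
|---|---|---|
| 0 | 20/22 = 90.9% (70.8-98.9) | 20/22 = 90.9% (70.8-98.9) |
| 2 | 18/20 = 90.0% (68.3-98.8) | 18/22 = 81.8% (59.7-94.8) |
| 5 | 15/17 = 88.2% (63.6-98.5) | 15/22 = 68.2% (45.1-86.1) |

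**5. Range over the assumptions.** Take *p* from 0.70 to 0.90, *f* from 0 to 0.50 and *s* from 2 to 8.

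- Smallest difference: 2 x (0.70 - 0.50)/22 = 0.018, about 2 points.
- Largest difference: 8 x (0.90 - 0)/22 = 0.327, about 33 points.
- With *s* = 0 the difference is nil.

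**The case against.** The strongest reply is that the investigators use the two words for one thing. Protocol 3.3 asks patients about symptoms and then calls the result patient-reported toxicity. Protocol 7.4.2 ties the in-person assessment to any symptom, while 10.3 describes the instrument as responding to any level of reported toxicity. Table 1 lists ordinary complaints such as fatigue, pain and cough, and its summary prevalence of 0.532 is what 6.1 describes as toxicity. If every documented symptom counts as toxicity, *s* is 0 and the estimate is correct. This objection stands as far as it goes: it makes the bias conditional. It does not remove the need for an edit, because the text does not equate the terms.

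A second reply is that protocol 7.1.1 gives the pilot's aim as to "optimize the questionnaire to quickly identify cancer related symptoms and immune related adverse events". If symptoms are also a target, a flagged symptomatic patient is not an error, and a symptom-free comparison group makes sense. But then the positive group would also have to be defined by symptoms. Either variable could serve; using one for sensitivity and another for specificity cannot be right if they differ. Protocol 3.3 names toxicity.

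The direction also depends on what counts as a negative screen. The Study Summary lets trial patients with minimal symptoms go straight to infusion, whereas 7.4.2 sends any identified symptom to a visit. These passages must be reconciled. Under the looser reading *f* exceeds 0 and the difference shrinks.

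Three stronger readings are tempting and are not supported:

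- **Specificity is biased upward, without qualification.** The documents do not show that any patient falls between the two groups.
- **The trial's 40% reduction in care time becomes unreachable.** With *s* = 2 and 2 others flagged, 18/47 = 38.3% of screens are negative; with 1 other flagged it is 19/47 = 40.4%. The crossing comes from a chosen number. The control mean and SD in 6.1 come from earlier care-time data, not from pilot specificity, and no specificity target is set.
- **Unfinished questionnaires distort specificity by a known amount.** Protocol 10.1 says of the trial: "Patients who do not fill out the questionnaire completely will therefore not be eligible to be fast-tracked". That rule is not carried over explicitly to the Aim 1 analysis, but the triage algorithm is in appendices that are not in the text reviewed. The Table 1 prevalences suggest item denominators that fall from 47 to 40, which could equally reflect missing EMR items.

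**Conclusion.** The point holds in a limited form. As written in three places, the specificity denominator is not the complement of the stated gold standard. If some patients have documented symptoms not recorded as toxicity, they are in neither estimate, and specificity is probably too high, since the instrument tends to flag them. If no such patients exist, or the two words are synonyms, the defect is one of wording only.

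The size is unknown. In the illustration (2 of 22 such patients, all flagged, plus 2 others flagged) the gap is 90.0% - 81.8% = 8.2 points, which is small beside an exact interval of 59.7-94.8%. It would nevertheless be a systematic error that a larger sample does not remove. Sensitivity, H1 and the precision statement in 6.1 do not depend on it.

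**What to change.** In the Study Summary, protocol 6.2 and SAP 1.2, derive both denominators from a single abstracted EMR variable, toxicity present or absent. Suggested text: *The denominator for specificity is every evaluable patient whose provider note records no toxicity, irrespective of any other symptom noted; the numerator is those of them whose e-triage screen was negative.* Report specificity among patients with no documented symptom as a secondary figure. If the two words are meant as synonyms, say so and use *toxicity* throughout.

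The cost is a few sentences in each document and no additional patients. If the terms do differ, the abstraction form needs separate fields for toxicity and other symptoms, which can be built in because the abstraction protocol is described as still to be developed. The downside is that the headline specificity may be somewhat lower.
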